13.5.6.2 Laboratory Parameters

Laboratory results (hematology, serum chemistry, coagulation parameters and urinalysis) will be classified according to NCI CTCAE v4.03 (or higher). Laboratory results not corresponding to an NCI CTCAE term will not be graded.

Shift tables will be shown for intra-individual changes from Baseline in NCI CTCAE grade for each study visit. Laboratory parameters will also be listed.

13.5.6.3 Vital Signs

Vital sign parameters (including blood pressure and heart rate) and body weight will be listed.

13.5.6.4 ECOG Performance Status

ECOG performance status will be listed. The ECOG Performance Scale is provided in [Appendix 5](#).

13.5.6.5 Physical Examination

Physical examination findings will be listed.

13.5.6.6 ECGs

ECG parameters will be described at each timepoint. The site will be required to review ECGs as a safety check. This will be done immediately by a qualified investigator or cardiologist at the study site. ECG assessments may be retained for review centrally, where results will be provided to the study site and retained as source data.

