5. 12-lead ECG measurements must be obtained at screening, pre-infusion on each treatment day, and at the treatment completion visit. The ECGs should be performed in triplicate (keeping the leads in place and patient supine during readings) and reviewed by the investigator or a qualified designee for safety and quality. The QTc interval should be calculated for each ECG using the Fridericia formula and averaged. Management of QT/QTc prolongation should be performed in accordance with institutional standard of care at the discretion of the treating physician. Digital and/or certified paper copies should be stored as part of the study documents in the event they need to be used in a future analysis.
6. At C1D1, C1D15, C3D1 and C3D15 12-lead ECG measurements should be performed 30-60 minutes pre-infusion and again 30-60 minutes post-infusion. The ECGs should be performed in triplicate (keeping the leads in place and patient supine during readings) and reviewed by the investigator or a qualified designee for safety and quality. The QTc interval should be calculated for each ECG using the Fridericia formula and averaged. Management of QT/QTc prolongation should be performed in accordance with institutional standard of care at the discretion of the treating physician. Digital and/or certified paper copies should be stored as part of the study documents in the event they need to be used in a future analysis.
7. Hematology includes white blood cell (WBC) count, differential WBC count, red blood cell count (RBC), hemoglobin, hematocrit and platelet count.
8. Serum chemistry includes sodium, potassium, magnesium, urea or blood urea nitrogen, creatinine, glucose, phosphate, total protein, albumin, adjusted calcium, total bilirubin, bicarbonate, chloride, uric acid, alkaline phosphatase, AST, ALT and LDH.
9. Either PT or INR may be measured, depending on institutional standards.
10. Urinalysis includes pH, specific gravity, ketones, leukocytes, protein, glucose, bilirubin, urobilinogen and occult blood. Dipstick testing is acceptable.

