2.5 Secondary Endpoints

The secondary endpoints are:

- Efficacy
 - Change from baseline in tumor size.
 - Duration of Overall Response (per RECIST).
 - Progression-Free Survival (per RECIST).
 - Time to Disease Progression (per RECIST).
 - Disease Control Rate (CR+PR+SD, per RECIST).
 - Best GCIG Overall Response, combining the change in CA125 from baseline with RECIST assessment (per GCIG criteria).
 - Overall Survival.
 - Assessment of ovarian cancer symptoms using the FOSI-18 questionnaire ([Appendix 3](#)).
- Safety
 - Treatment-emergent adverse events (per NCI CTCAE v4.03).
 - Clinically-significant laboratory parameters (per NCI CTCAE v4.03).
 - Changes in vital signs and serial ECGs.

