13.5.5 PRO Analysis

13.5.5.1 EQ-5D-5L

Descriptive statistics, graphs and listings will be reported for health state utility values and visual analogue scale by visits as well as change in these scores from baseline. Further details will be included in the SAP.

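### A secondary safety endpoint is change in vital signs and ECGs, but the protocol plans only a listing for vital signs and by-timepoint ECG description, with no change analysis named

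*Protocol*

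**What the plan says.** The synopsis and section 2.5 list among the secondary safety endpoints "Changes in vital signs and serial ECGs".

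The planned analyses are in section 13.5.6:

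- Vital signs (13.5.6.3): "Vital sign parameters (including blood pressure and heart rate) and body weight will be listed".
- ECGs (13.5.6.6): "ECG parameters will be described at each timepoint". The section adds that "The site will be required to review ECGs as a safety check" and allows for possible central review.
- Laboratory parameters (13.5.6.2), for comparison: "Shift tables will be shown for intra-individual changes from Baseline in NCI CTCAE grade for each study visit", followed by a listing as well.

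Section 13.5.5.1 likewise asks for EQ-5D-5L scores by visit "as well as change in these scores from baseline".

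The ECG schedule is in the Summary Schedule of Events, note 6, and is repeated in sections 5.5.1 and 5.5.4: "At C1D1, C1D15, C3D1 and C3D15 12-lead ECG measurements should be performed 30-60 minutes pre-infusion and again 30-60 minutes post-infusion". Each recording is a triplicate, and "The QTc interval should be calculated for each ECG using the Fridericia formula and averaged".

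**The concern.** The endpoint is worded as change, and the text that should deliver it never mentions change. For vital signs the stated output is a listing, which shows individual values but estimates nothing. For ECGs the stated output is a description at each timepoint. That does not commit the sponsor to any within-patient comparison, even though pre- and post-infusion readings are taken close together in the same patient.

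The question at stake is whether QTcF moves after infusion or over repeated cycles, and in how many patients it moves a lot. The protocol treats QT as relevant: it excludes patients with QTc above 450 ms and bars QT-prolonging drugs (sections 4.2 and 10.4). Two columns of timepoint means do not answer the question about individual patients.

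**Working it through.** **1. Endpoint set against analysis.** The protocol has no figure to reproduce here, so the check is mainly textual.

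| Item | Named as an endpoint in 2.5 or 2.7? | Change analysis named? | Stated output |
|---|---|---|---|
| Laboratory parameters | Yes (clinically significant values) | Yes, within patient from baseline | Shift tables and listing |
| EQ-5D-5L | Yes (exploratory) | Yes, from baseline | Descriptive statistics, graphs, listings |
| Vital signs | Yes, as change | No | Listing |
| ECGs | Yes, as change | No | Description by timepoint |
| ECOG status, physical examination | No | No | Listing |

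Vital signs, a declared change endpoint, get the same treatment as two items that are not endpoints. The laboratory section separates a change summary from a listing, so the document does not treat them as the same thing. Neither 13.5.6.3 nor 13.5.6.6 says from which reading a change would be measured.

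**2. What same-day timepoint summaries can and cannot show.** If the same patients have both readings, the difference between the post- and pre-infusion means equals the mean within-patient change. That much is recoverable. The spread is not, because it depends on the within-patient correlation ρ:

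SD(change) = SD × √(2(1 − ρ)), with equal SD at both timepoints.

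The protocol gives neither SD nor ρ, so both are assumed. The last column further assumes normality. It gives the share of patients whose change exceeds the mean change by at least one single-timepoint SD, P(Z > 1/√(2(1 − ρ))).

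| ρ (assumed) | SD(change)/SD | SD(change) if SD = 15 ms | SD(change) if SD = 20 ms | Share of patients |
|---|---|---|---|---|
| 0.3 | 1.18 | 17.7 ms | 23.7 ms | 20% |
| 0.5 | 1.00 | 15.0 ms | 20.0 ms | 16% |
| 0.7 | 0.77 | 11.6 ms | 15.5 ms | 10% |
| 0.9 | 0.45 | 6.7 ms | 8.9 ms | 1% |

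All four rows produce identical timepoint means and SDs. With 44 patients at the selected dose, the last column runs from about 9 patients (0.20 × 44 = 8.8) to about 1 (0.013 × 44 = 0.6). Timepoint summaries cannot tell these cases apart.

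**3. Across cycles.** Cycles last 28 days, so Cycle 3 Day 1 falls after 2 × 28 = 56 days, or 8 weeks. The first on-treatment scan is also due 8 weeks from Cycle 1 Day 1 (±7 days), and treatment stops at RECIST progression. Patients who progress at that scan will generally not supply Cycle 3 ECGs. A Cycle 3 mean set beside a Cycle 1 mean therefore compares different groups of patients, and the difference mixes change with drop-out. This does not apply to same-day pairs.

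**The case against.** The strongest reply is that section 13 describes itself as giving main features only, with the detail to follow in a SAP that is not at hand. Section 13.5.6 allows further safety analyses at any time. Section 13.2 promises that all available safety data will be tabulated as well as listed. Describing ECGs at each timepoint sets how often they are described and does not restrict the description to raw values. No objective names a QT effect, and the protocol's stated uses for the ECGs are review for safety and quality and storage for possible later analysis. Clinically significant findings would also surface as adverse events.

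Much of this stands. A reader might infer that the ECG change endpoint goes unanalysed and that the paired readings are wasted. The protocol does not support that: change summaries are not excluded, sites review the tracings, copies are kept, and the mean same-day change can be recovered.

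A reader might also infer a loss of precision. With SD 20 ms, ρ = 0.7 and n = 44, the standard error of the difference is 20 × √(2/44) = 4.26 ms unpaired and 20 × √(2 × 0.3/44) = 2.34 ms paired. The arithmetic is right, but the SD and ρ are assumed, fewer than 44 patients may contribute at Cycle 3, and the protocol plans no unpaired inference. It is not a measure of harm here.

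What does not stand is that nothing needs changing. For vital signs the protocol states the output, and it is a listing. The general sentence in 13.2 does not name change, and permission to add analyses does not prespecify a declared endpoint. Where the authors meant to defer detail to the SAP, as for both questionnaires and the biomarkers, they usually said so; 13.5.6.3 and 13.5.6.6 do not.

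**Conclusion.** The point holds as a mismatch between a declared endpoint and its stated analysis. It is plain for vital signs, where the text offers a listing for a change endpoint. It is weaker for ECGs, where the text is silent on change but does not rule it out.

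The practical loss, if the text is followed literally, is a missing change summary for vital signs, no within-patient spread or count of large QTcF increases, and cross-cycle comparisons affected by drop-out. The textual part rests on no assumption. The table of change SDs rests on assumed correlations and SDs and only illustrates how much timepoint summaries leave open. The consequence is minor: it concerns descriptive safety output, can be repaired from data already planned, and does not touch the primary endpoint.

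**What to change.** - **Section 13.5.6.3:** keep the listing and add a summary of change from baseline in vital signs by visit and dose.
- **Section 13.5.6.6:** summarise within-patient change in triplicate-mean QTcF by dose in two ways. The first is from a defined baseline, for example the Cycle 1 Day 1 pre-infusion reading. The second is the same-day post-minus-pre-infusion difference at each of the four paired occasions. Restrict each summary to patients with both readings and show their number.
- **Counts:** add the number of patients exceeding prespecified QTcF values and prespecified increases. The protocol contains no analysis cut-offs or confidence level for this, so the sponsor should choose them and record them before the data are reviewed.
- **Baseline:** define it once for each of the two components.

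The cost is a few sentences and a few descriptive tables. No visit, recording or sample is added.

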13.5.6.7 Pharmacokinetics

The PK of single and multiple-dose NUC-1031 will be assessed, including:

- Maximum concentration (C_{max})
- Area under the curve (AUC)
- Half-life ($T_{1/2}$)
- Volume of distribution (V_d)
- Clearance (CL).

PK of the following will be measured:

- In plasma/urine: NUC-1031, dFdC and dFdU.
- In peripheral blood mononuclear cells: NUC-1031, dFdC, dFdCMP, dFdCDP, dFdCTP and dFdU.

All above PK parameters will be analyzed in the PK population.

13.5.6.8 Exploratory Endpoints

Assessment of candidate genomic, transcriptomic and proteomic biomarkers of resistance/sensitivity to NUC-1031 in tumor specimens will be analysed in the ITT population. The candidate genomic, transcriptomic and proteomic biomarkers will be defined in the SAP.

13.5.7 Primary Analysis and Interim Analyses

The primary analysis of Part II will take place when 44 patients are enrolled at the selected dose and all active patients have undergone the required assessments for assessment of confirmed ORR by RECIST (*i.e.*, approximately 16 weeks after the 44th patient starts treatment).

Up to three interim analyses may be performed during Part I in order to select a dose to take forwards into Part II. For the purpose of the dose selection analyses only, unconfirmed responses may be taken into account, provided that the response is unconfirmed due to insufficient follow-up data being available, rather than because the subsequent data is available and does not confirm the initial response.

An additional efficacy update analysis may be performed following the primary analysis of Part II. The purpose of this analysis would be to provide more mature efficacy data. As such, the timing of such an analysis, if required, will be determined following review of the primary analysis.

Timings of all analyses will be described in the statistical analysis plan. Upon review of the data from Part II by the DSMC, the study may be further expanded at the selected dose level, which will be described in a protocol amendment.

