2.2 Secondary Objectives

The secondary objectives are:

- To assess additional measures of anti-tumor activity of NUC-1031 including:
 - Change from baseline in tumor size.
 - Duration of Overall Response (per RECIST).
 - Progression-Free Survival (per RECIST).
 - Time to Disease Progression (per RECIST).
 - Disease Control Rate (CR+PR+SD, per RECIST).
 - Best GCIG Overall Response, combining the change in CA125 from baseline with RECIST assessment (per GCIG criteria).
 - Overall Survival.
- To further assess the safety profile of NUC-1031 administered over multiple cycles.
- To explore relationships between NUC-1031 PK, pharmacodynamics and clinical activity.
- To describe the effects of NUC-1031 on ovarian cancer symptoms.

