3 INVESTIGATIONAL PLAN

3.1 Overall Study Design

This is a randomized open-label, two-part clinical study of NUC-1031 in up to 64 patients with platinum-resistant ovarian cancer. Patients will be randomized to NUC-1031 500 mg/m² or 750 mg/m² and will be evaluated in two parallel cohorts of up to 20 patients each in Part I of the study. The randomization will be stratified to ensure that key prognostic markers, including BRCA mutation status and number of prior lines of chemotherapy (3 or >3), are balanced between the 2 dose levels. The stratification procedure will be defined in the statistical analysis plan.

On the basis of ongoing safety, dosing intensity, PK and clinical activity observed during Part I, one dose level will be selected for further evaluation in Part II of the study, where enrollment shall continue until a total of 44 response evaluable patients are recruited at the selected dose (Figure 1).

[figure not shown]

Figure 1 PRO-105 Study Schema

The primary analysis of response rate will take place when 44 patients are enrolled at the selected dose and all active patients have undergone the required assessments for assessment of confirmed ORR by RECIST (*i.e.*, approximately 16 weeks after the 44th patient starts treatment). Upon review of these data from Part II by the DSMC, the study may be further expanded at the selected dose level, which will be described in a protocol amendment. An efficacy update analysis may also be performed to provide more mature efficacy data.

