12.13 Data Safety Monitoring Committee (DSMC)

The DSMC will review the safety, dosing intensity, pharmacokinetic and clinical activity data from Part I of the study to decide on which dose should be used in Part II. Members of the DSMC will include:

- Chief Investigators from the US and Europe
- Selected Principal Investigators from participating sites
- Chiltern Medical Monitors
- NuCana Medical Director
- Study management staff from NuCana.

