13.1 Sample Size

The primary analysis of response rate will take place when 44 patients are enrolled at the selected dose and all active patients have undergone the required assessments for assessment of confirmed ORR by RECIST. The study will be considered to have met its primary endpoint if a minimum of 4 confirmed responses (CR or PR) is observed. Based on 44 patients, if the true ORR is 15%, there is greater than an 80% probability of observing 4 or more responses. Furthermore, if the true response rate were only 5%, there would be less than a 7% probability of observing 4 or more responses.

Upon review of the data from Part II by the DSMC, the study may be further expanded at the selected dose level, which will be described in a protocol amendment.

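### The success probabilities in 13.1 and the synopsis are for one fixed sample of 44, but up to 20 of the 44 are Part I patients whose responses may help choose the dose

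*Protocol*

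**What the plan says.** Protocol 3.1 describes two randomized dose groups that "will be evaluated in two parallel cohorts of up to 20 patients each in Part I of the study". It continues: "On the basis of ongoing safety, dosing intensity, PK and clinical activity observed during Part I, one dose level will be selected". After that, "enrollment shall continue until a total of 44 response evaluable patients are recruited at the selected dose". The synopsis adds that the primary objective is assessed in those 44 patients, and total enrollment is capped at 64.

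Section 12.13 gives the choice of dose to the committee: "The DSMC will review the safety, dosing intensity, pharmacokinetic and clinical activity data from Part I of the study". No weights are attached to the four criteria. Section 13.5.7 says: "Up to three interim analyses may be performed during Part I in order to select a dose to take forwards into Part II". Sections 13.3 and 13.5.7 let unconfirmed responses count towards dose selection; 13.5.7 limits this to responses that are unconfirmed only because follow-up is still too short.

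Section 13.1 sets success at a minimum of 4 confirmed responses. It then gives the operating characteristics: "Based on 44 patients, if the true ORR is 15%, there is greater than an 80% probability of observing 4 or more responses", and "if the true response rate were only 5%, there would be less than a 7% probability of observing 4 or more responses". The synopsis repeats both. Neither place says how dose selection affects these figures.

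**The concern.** The patients who help choose the dose are counted again in the test of that dose. A dose that did well in Part I partly by chance is more likely to be carried forward, and its lucky responses stay in the total of 44. A binomial calculation for 44 patients describes a trial without that step.

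The printed 5% and 15% probabilities are how a reader will judge the primary result, and the DSMC considers expansion of the study on review of the same data. If the sponsor corrects only the threshold, the new figures would still describe a design without dose selection.

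**Working it through.** **Inputs.** 44 patients at the selected dose (synopsis, 3.1). Up to 20 per dose in Part I (3.1). Maximum enrollment 64 (3.1). Success at 4 or more confirmed responses (13.1). True ORRs of 5% and 15% (13.1).

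**How many of the 44 are Part I patients.** 64 = 20 + 20 + 24 and 44 = 20 + 24. The cap of 64 therefore fits the Part I patients at the selected dose being part of the 44.

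**Step 1: the plan's own figures, fixed sample.** X ~ Bin(44, p).

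- p = 5%: P(X = 0, 1, 2, 3) = 0.1047, 0.2424, 0.2743, 0.2021. P(X ≥ 4) = 1 − 0.8235 = 17.7%. P(X = 4) = 0.1090, so P(X ≥ 5) = 6.7%.
- p = 15%: P(X ≥ 4) = 91.3%. P(X = 4) = 0.1032, so P(X ≥ 5) = 81.0%.

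The printed pair (above 80%, below 7%) fits 5 or more. For the stated rule of 4 or more, the 5% figure is wrong before dose selection enters.

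**Step 2: response alone decides.** Assume equal true ORRs, 20 per dose, and selection responses equal to confirmed BICR responses. Let a and b be the Part I counts, each Bin(20, p), and M = max(a, b). Then P(M ≤ m) = F(m)², where F is the Bin(20, p) distribution function. The 24 later patients contribute Y ~ Bin(24, p), and

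P(success) = Σ P(M = m) × P(Y ≥ r − m).

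For p = 5% and r = 4: F(0), F(1), F(2), F(3) = 0.3585, 0.7358, 0.9245, 0.9841. Squaring and differencing gives P(M = 0, 1, 2, 3) = 0.1285, 0.4129, 0.3133, 0.1137 and P(M ≥ 4) = 0.0315. P(Y ≥ 4, 3, 2, 1) = 0.0298, 0.1159, 0.3392, 0.7080. The sum is 0.0038 + 0.0479 + 0.1063 + 0.0805 + 0.0315 = 0.270.

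The same calculation gives:

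| Both doses truly at | Threshold | Selection independent of response | Response alone |
|---|---|---|---|
| 5% | 4 or more | 17.7% | 27.0% |
| 5% | 5 or more | 6.7% | 11.2% |
| 15% | 4 or more | 91.3% | 97.2% |
| 15% | 5 or more | 81.0% | 91.4% |

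**Step 3: bias of the pooled ORR.** Bias = (E[M] − 20p)/44. At 5%: (1.513 − 1)/44 = 1.2 points. At 15%: (3.884 − 3)/44 = 2.0 points.

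**Step 4: why the right-hand column is a maximum.** Whatever the rule, the chosen dose's Part I count cannot exceed M, and the later patients are independent of it. With both doses at the same true ORR and at most 20 per dose, no selection rule can exceed the response-alone figure. A simulation of three looks at 7, 14 and 20 per dose gave 26.0% to 27.0% (5%, 4 or more), which agrees within simulation error.

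**Step 5: weaker influence or a smaller Part I**, both doses at 5% (4 or more / 5 or more):

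| Rule | 20 per dose | 10 per dose |
|---|---|---|
| Response decides only if the doses differ by 2 or more responses | 23.8% / 10.0% | 20.3% / 8.2% |
| Response alone | 27.0% / 11.2% | 23.8% / 9.8% |

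With 20 per dose, the first rule is decided by response in 25% of cases. If selection responses agree imperfectly with confirmed BICR responses (assumed: 80% of later confirmed responders and 5% of the others counted at selection), response alone with 20 per dose gives 23.6% / 9.7%.

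**The case against.** **The size is not fixed by the protocol, and it may be zero.** Safety, dosing intensity and PK also drive the choice. If the choice is independent of response, the binomial figures hold. This stands, and it is why the result is a range with 17.7% / 6.7% at its lower end. Leaving response out of the choice would not by itself guarantee independence, since PK may be related to response; a secondary objective is "To explore relationships between NUC-1031 PK, pharmacodynamics and clinical activity".

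**The statement is conditional and the pooling is open.** Section 13.1 says what follows for 44 patients at a given true ORR and names no type I error. That is fair, and pooling is a legitimate choice. Still, the figures are offered as the properties of this study's success rule, and nothing tells the reader that they leave out a step of the design.

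**The bias is small against the sampling error.** At most 1.2 points at 5% and 2.0 at 15%, against an exact 95% interval of 6.6% to 30.1% for, say, 7/44. This stands for estimation. The effect on the chance of success at 5% is larger.

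**Selection also helps.** It raises the chance of success at a true 15% as well. This stands, and any restatement should show both.

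**A stronger reading to avoid.** Suppose the true ORRs are 15% and 5% and response alone decides. If the 5% dose is chosen, it meets 4 or more in 39.7% and 5 or more in 18.9%. A reader might infer that 27.0% / 11.2% is therefore not a maximum. That compares different probabilities. The 5% dose is chosen in only 14.6% of cases, so the chance that it is chosen and succeeds is 0.146 × 0.397 = 5.8%, or 0.146 × 0.189 = 2.7%.

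**Conclusion.** The point holds as one of disclosure. The printed probabilities belong to a fixed sample of 44, whereas the design can reuse up to 20 patients whose responses helped choose the dose. With both doses at 5%, the chance of success lies between 17.7% (choice independent of response) and a maximum of 27.0% for 4 or more, and between 6.7% and 11.2% for 5 or more. With both at 15%, it lies between 91.3% and 97.2%, and between 81.0% and 91.4%. These ranges assume equal true ORRs and 20 per dose. The upper ends are reached only if response alone decides and selection responses equal confirmed BICR responses.

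A reader might infer that the true error rate is 27.0%, that three looks multiply it, or that the pooled analysis is invalid. The protocol supports none of these: it gives no weights for the criteria, the looks serve dose selection only and stay within the same bound, and the pooled analysis needs only properly described properties.

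The mismatch between 17.7% and the printed bound of 7% is a separate and certain error that does not depend on selection. It should be settled first. The selection point is lower in priority and worth correcting when those sentences are reopened.

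**What to change.** 1. Reconcile the success threshold with the printed probabilities in 13.1 and the synopsis.
2. In both places, add a sentence such as: These probabilities are for a fixed sample of 44 and do not allow for the use of Part I responses in choosing the dose.
3. Beside it, give the range for the adopted threshold at both true rates: 17.7% to 27.0% and 91.3% to 97.2% for 4 or more, or 6.7% to 11.2% and 81.0% to 91.4% for 5 or more. State the assumptions: equal true ORRs, 20 per dose, selection responses equal to confirmed BICR responses, and selection ranging from independent of response to response alone. The upper figures may be called the maximum for two doses with the same true ORR and at most 20 per dose. If the 15% and 5% case is also shown, label it as conditional on the 5% dose being chosen.
4. Keep the pooled 44-patient primary analysis and the selection criteria.

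A supportive ORR with exact interval in patients enrolled after dose selection is optional and may be left to the SAP. It would rest on at least 44 − 20 = 24 patients and be imprecise (4.7% to 37.4% for 4/24).

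The cost is wording in two places and at most one small table, with no extra patients. The stated error rate will look less favourable.
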